7.7.2.2 Procedures Required During Dosing Period

During each cycle, the following testing and procedures are required:

Vital Signs: Blood pressure, heart rate, respiration rate, body temperature, and pulse oximetry during dosing period (usually Days 1, 2, 3, 4 and 5) and Days 8, 15, and 22. Heart rate (HR), temperature, respiratory rate (RR), blood pressure (BP) to be taken pre- SL-401 infusion, at end of SL-401 infusion, every 30 minutes for 4 hours following the end of infusion and as clinically indicated for all doses of the Run-in Cycle. For Cycle 1 and thereafter, vital signs are to be taken pre-infusion, at end of infusion and as clinically indicated. For temperature > 38°C, obtain blood cultures (2 sets) and collect urine for urinalysis and culture.

Diagnostic Tests:

- During dosing period, prior to SL-401 infusion (usually Days 1, 2, 3, 4, 5) and Days 8, 15, and 22: complete blood count (CBC) with differential, platelets, sodium, potassium, chloride, bicarbonate, blood urea nitrogen (BUN), creatinine, glucose, total protein, albumin, calcium, phosphorus, uric acid, total bilirubin, ALT, AST, alkaline phosphatase, lactate dehydrogenase (LDH), CPK, prothrombin time (PT) / International Normalized Ratio (INR), and partial thromboplastin time (PTT).
- Days 1 (prior to SL-401 infusion): routine urinalysis
- For temperature ≥ 38°C, draw blood culture × 2, and collect urine for urinalysis and culture/
- Daily weight (during the period of the 5 infusions) and Days 8, 15 and 22.

The results of these evaluations may result in withholding of a scheduled SL-401 infusion, largely based on unresolved manifestations of fluid retention and/or other relevant acute toxicities during daily dosing, are described below and in Table 11.

7.7.2.3 Events Requiring Holding of SL-401

Withhold SL-401 infusion if any of the following occur:

- Body temperature ≥ 38°C
- HR ≥ 130 or ≤ 40 bpm
- Systolic BP ≥ 160 or ≤ 80 mmHg
- Serum creatinine > 1.8 mg/dL
- Serum albumin < 3.0 g/dL (SL-401 will be withheld for the remainder of the study cycle).
- AST > 5 × the ULN or ALT > 5 × the ULN (SL-401 will be withheld for the remainder of the study cycle).
- Increase in body weight by ≥ 1.5 kg over weight (pre-treatment) on the prior treatment day.

In situations where SL-401 administration is postponed because of deviations in vital signs, weight or laboratory values outside of the above parameters, SL-401 may be re-administered subsequently, pending normalization of the abnormalities and pending evidence of stabilization of the underlying clinical conditions resulting in these abnormalities, as detailed below. As indicated in Section 7.3.3, postponed doses may be administered within a 10-day period following the initial day of treatment within a cycle.

In the setting of temperature ≥ 38°C, SL-401 may be administered pending resolution, provided that an appropriate evaluation for infectious etiologies has been undertaken, and provided that the Investigator determines that there is minimal likelihood of uncontrolled systemic infection including sepsis; this may occur on the same day as the temperature elevation, or on subsequent days.

In the setting of delays secondary to findings consistent with capillary leak syndrome (i.e., in the setting of resolved hypotension, tachycardia, increased weight, or albumin reductions of a magnitude lower than those warranting withholding of SL-401 for the duration of a given cycle), subsequent SL-401 infusions are to be administered pending determination by the Investigator that there is no/minimal evidence of ongoing capillary leak syndrome and pending discussion with the study Medical Monitor. Any subsequent SL-401 infusions are to be administered on days subsequent to the identification of the abnormality (i.e., not the same day the abnormality was identified).

In settings in which albumin is reduced to <3.0g/dL or in which albumin is reduced by more than 1.0 g/dL below the level at the start of the cycle (i.e. from 4.3g/dL to 3.2g/dL), no subsequent SL-401 will be administered for the duration of the cycle.

In settings in which transaminases (AST/ALT) are elevated to > 5 X ULN, no subsequent SL-401 will be administered for the duration of the cycle.

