Doses of SL-401 may be held for criteria specified in Section 7.7.2, Table 11, concerning abnormalities in vital signs, serum creatinine, albumin, AST/ALT or increases in body weight; in the setting of these abnormalities, 5 doses may be given over 10 days; otherwise no dose modifications are permitted during the Run-in Cycle or Cycle 1 (initial cycle of combination therapy) unless the patient experiences a DLT. No dose escalations are permitted in any given patient once a dose level has been assigned. Patients experiencing DLT during the Run-in Cycle will be discontinued from study. Patients experiencing DLT

during Cycle 1 (initial cycle of combination therapy) may continue on therapy, if toxicity can be managed according to the dose modification guidelines outlined below and the patient has not experienced disease progression; the DLT event will nonetheless contribute to the assessment of MTD for that given cohort.

Dose modifications may be performed in all subsequent cycles of treatment. If toxicities cannot be managed by dose modification or the patient cannot tolerate the lowest dose of study drug, the patient is to be discontinued from study drug unless there is evidence of disease stabilization or response beyond the initial treatment cycle. However, patients that have achieved a plateau of response to study therapy will continue to adhere to the schedule of assessments followed during the treatment phase of the study even though study drug has been discontinued.

Dose Modification Guidelines are detailed in Section 7.7.

Safety Assessments:

Safety assessments include DLTs, AEs, serious adverse events (SAEs), physical examinations, vital sign measurements, clinical laboratory evaluations, and reasons for treatment discontinuation due to toxicity. The AE reporting period for a patient treated in the study begins with the initiation of SL-401 (or SL-401/POM/DEX in phase 2) and is continuous through 30 days after the last dose of SL-401 or SL-401/POM/DEX. All AEs that occur in treated patients during the AE reporting period specified in the protocol must be reported to the Sponsor, whether or not the event is considered related to SL-401/POM/DEX. Any known untoward event that occurs beyond the AE reporting period that the Investigator assesses as related to SL-401/POM/DEX should also be reported as an AE.

Efficacy Assessments:

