5.2 Patient Inclusion Criteria

Eligible patients will be considered for inclusion if they meet all of the following criteria. (All necessary baseline studies for determining eligibility must be obtained within 21 days or as indicated in the Schedule of Events [Table 13] prior to enrolment).

- Male or female patient who is at least 18 years of age.
- Patient has given voluntary written informed consent before performance of any studyrelated procedures not part of standard (non-investigational) medical care.
- 3. Patient has been previously diagnosed with MM based on standard criteria.
- Patient has received:
 - a. at least 2 prior therapies including a proteasome inhibitor (≥ 2 cycles) and lenalidomide (≥ 2 cycles), and
 - b. has achieved at least stable disease (SD) for ≥ 1 cycle of treatment on ≥ 1 prior treatment, and
 - has demonstrated disease progression subsequent to treatment, during or within 60 days following completion of the most recent therapy
- Patient has an Eastern Cooperative Oncology Group (ECOG) performance status score < 2.
- Patients has measurable disease defined as at least one of the following:
 - Serum monoclonal (M) protein ≥ 0.5 /dL (≥5 g/L).
 - b. Urine M protein ≥200 mg/24 hours.
 - c. Serum free light chain (FLC) assay: involved FLC ≥10 mg/dL (≥100 mg/L) and an abnormal serum FLC ratio (<0.26 or >1.65).
- Clinical Laboratory Inclusion Criteria: The following laboratory results must be met within 14 days prior to study drug (treatment) administration:
 - a. Absolute neutrophil count (ANC) ≥ 1000 cells/µl (growth factor cannot be used within the previous 7 days)
 - b. AST and ALT $\leq 2.5 \times$ upper limit of normal (ULN)
 - Platelet count ≥ 50,000/µl (without platelet transfusion in the previous 7 days)
 - d. Total bilirubin ≤ 1.5 mg/dL

- e. Serum creatinine ≤ 2.0 mL/dL and creatinine clearance ≥ 40 mL/min (calculated by the Cockcroft-Gault Equation or per 24 hour urine collection).
- f. Serum albumin $\geq 3.2 \text{ g/dL}$.
- g. Serum creatine phosphokinase (CPK) ≤ 2.5 × the ULN.
- h. Serum calcium (corrected for albumin) level at or below the ULN range (treatment of hypercalcemia is allowed and subject may enroll if hypercalcemia returns to normal range with standard treatment).

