6.2.2 Dose limiting Toxicity Definition

Run-In Cycle

In order to be evaluable for DLT assessment during the Run-in Cycle of single agent SL-401, a patient must receive all 5 doses within a 10 day time period (Days 1 – 10) and complete the 28 days of observation unless they experience DLT (patients who discontinue prior to this juncture because of disease progression or for reasons unrelated to study therapy will be replaced).

Combination Therapy Initial Cycle (Cycle 1)

In order to be evaluable for DLT assessment in Cycle 1 (initial cycle of combination therapy), a patient must receive at least 3 infusions of SL-401 and 16 (approximately 75%) doses of POM during Cycle 1, and complete the 28 days of observation unless they experience DLT. (Patients who discontinue prior to this juncture because of disease progression or for reasons unrelated to study therapy will be replaced).

The period of evaluation for DLT will include Run-in Cycle and Cycle 1 (the initial cycle of combination therapy).

DLT is defined as any of the following treatment-emergent adverse events (TEAEs) that are possibly, probably, or definitely related to therapy occurring in the first cycle:

- Any ≥ grade 4 neutropenia lasting greater than 7 days or ≥ grade 3 neutropenia associated with fever.
- Any grade ≥ 4 thrombocytopenia lasting greater than 7 days or ≥ grade 3 thrombocytopenia associated with bleeding.
- Any ≥ grade 3 non-hematologic toxicity except:
 - Grade 3 nausea, vomiting, or diarrhea lasting no longer than 48 hours (with resolution to ≤ grade 1 or baseline) with optimal supportive care.
 - Grade 3 arthralgia, myalgia, fever, in the absence of neutropenia, lasting no longer than 48 hours (with resolution to ≤ grade 1 or baseline).
 - Grade 3 fatigue lasting < 7 days.
 - Grade 3 laboratory abnormalities that are asymptomatic and not considered clinically significant by the Investigator, that respond to or do not require intervention and resolve to ≤ grade 1 or baseline ≤ 28 days after the last infusion of SL-401.
- Grade 4 transaminase or CPK elevation (confirmed within 24 hours of initial identification) regardless of duration or relationship to SL-401.

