Grade 1 or 2 non-hematologic A/E, regardless of drug attribution, do not require dose modifications, unless in the opinion of the Investigator, the event is intolerable and warrants dose modification in consultation with the Medical Monitor.

SL-401 Adverse events that require holding SL-401 (all treatment cycles)

Heart rate ≥ 130 or ≤ 40 bpm	Investigate and address potential etiologies of tachy/bradycardia.
Systolic BP ≥ 160 or ≤ 80 mmHg	Hypertension : administer antihypertensive therapy as appropriate. Hypotension : evaluate potential capillary leak syndrome; administer parenteral hydration/electrolyte support as appropriate (refer to Section 7.7.3.3).
Serum creatinine > 2.0 mg/dL	Evaluate potential etiologies of renal dysfunction; parenteral hydration/electrolyte support as appropriate.
Serum albumin < 3.0 g/dL	Evaluate potential capillary leak syndrome. Administer parenteral (IV) albumin as indicated in protocol Section 7.7.3.3. Withhold subsequent SL-401 for the duration of the cycle.
Reduction in serum albumin by more than 1.0g/dL below level at the start of the current cycle (i.e. from 4.3g/dL to 3.2g/dL)	Evaluate potential capillary leak syndrome. Administer parenteral (IV) albumin as indicated in protocol Section 7.7.3.3. Withhold subsequent SL-401 for the duration of the cycle.
AST $> 5 \times$ the ULN or ALT $> 5 \times$ the ULN	Ongoing observation of clinical, laboratory and other parameters of hepatic dysfunction. Withhold subsequent SL-401 for the duration of the cycle.
Body temperature ≥ 38°C	Evaluate potential etiologies of fever, including infectious complications. Administer anti-pyretic therapy (i.e., acetaminophen/paracetamol) as appropriate.

CTCAE Category	Agents	Toxicity During a Cycle
Increase in body weight by \geq 1.5 kg over weight (pretreatment) on the prior treatment day.		Evaluate potential capillary leak syndrome. Evaluate for fluid retention or other potential etiologies of weight gain. Diuresis as appropriate.

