7.8 Guidelines for Initiation of a New Cycle of Therapy

For a new cycle of treatment to begin, the patient must meet the following criteria:

- ANC must be ≥ 1,000/mm³.
- Platelet count must be ≥ 50,000/mm³.
- All other non-hematologic SL-401 related toxicity must have resolved to ≤ grade 1 or to the patient's baseline condition.
- The patient does not have any adverse events that require holding SL-401 (Table 11) or has not had prior anaphylaxis or ≥ grade 3 hypersensitivity reaction.
- All other non-hematologic POM/DEX related toxicity must have resolved to ≤ grade 2 or to the patient's baseline condition.

If the patient fails to meet the above-cited criteria for initiation of the next cycle of treatment, dosing should be delayed for 1 week. At the end of that time, the patient should be re-evaluated to determine whether the criteria have been met. If the patient continues to fail to meet the above-cited criteria, within 14 days from a scheduled day one of therapy, then discontinue treatment. In patients in whom there may be evidence of MM response or stability as determined by the treating physician, treatment may be resumed at a reduced SL-401/POM/DEX dose level after discussion with the Medical Monitor.

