- Hematology: CBC to be performed and reviewed by clinician prior to SL-401 dosing on Days 1 5 and Days 8, 15 and 22 or as clinically indicated. The Run in and Cycle
 1, Day 1, results must remain within the entry criteria values to initiate therapy.
- g. Serum Chemistry: to be performed and reviewed by clinician prior to SL-401 dosing on Days 1 5 and Days 8, 15, and 22 or as clinically indicated. The Run in and Cycle 1 Day 1 results must remain within the entry criteria values to initiate therapy. Chemistry includes: glucose (fasting at baseline), albumin, total protein, AST, ALT, bilirubin

- (total and direct), alkaline phosphatase, LDH, CPK, sodium, potassium, chloride, bicarbonate/carbon dioxide, calcium, magnesium, phosphate, uric acid, BUN, serum creatinine and estimated creatinine clearance (Cockroft-Gault formula Appendix 15.7). Albumin, transaminases (AST/ALT) and creatinine must be evaluated prior to each SL-401 dose.
- Urinalysis: Appearance, color, pH, specific gravity, ketones, leukocytes, protein, glucose, bilirubin, urobilinogen, and occult blood. To be performed at baseline, during the treatment period as clinically indicated and EOT.
- i. Plasmacytoma Assessment Disease: For patient with known or suspected plasmacytomas, assess by physical exam and/or radiologic evaluation at baseline and as clinically indicated. Disease that can be assessed by physical exam should be evaluated on Day 1 of each cycle. Disease that can be assessed by radiologic evaluation should be assessed according the IMWG criteria for evaluation of response. This may include computerized tomography (CT) scan, ultrasound, PET/CT or MRI. The same method of assessment should be used at each evaluation for any individual patient. Assess the need to evaluate for suspected new, worsening, or improved plasmacytomas to confirm response or progression every cycle. Evaluations may be performed on Day 1 of a cycle or during the 7 days prior to Day 1 of the Cycle as needed for scheduling.
- j. Skeletal Survey: Plain film X-rays to including skull, vertebrae, all long bones, pelvis and chest are required. PET/CT MRI may be done to supplement X-rays of any disease site at Investigators discretion. Also required at any time when clinically indicated, for suspected progression per IMWG response criteria.

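### The serum creatinine limit for holding an SL-401 infusion is 1.8 mg/dL in Section 7.7.2.3 but 2.0 mg/dL in the synopsis and Table 11, and nothing says which governs

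*Protocol*

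**What the plan says.** Three lists in the current text state when an SL-401 infusion must be held for creatinine:

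- Section 7.7.2.3: "Serum creatinine > 1.8 mg/dL".
- Table 11 in Section 7.7.2, in the block on SL-401 holds that applies to all treatment cycles: "Serum creatinine > 2.0 mg/dL".
- Synopsis, Study Treatment: the same limit as Table 11.

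The cross-references do not rank them. Section 7.7 cites 7.7.2.2, 7.7.2.3 and Table 11 together for the Run-in Cycle and Cycle 1 of phase 1. Section 7.7.2.2 says that the grounds for withholding "are described below and in Table 11". The synopsis, under Dose Modification, sends the reader to Table 11 alone: "Doses of SL-401 may be held for criteria specified in Section 7.7.2, Table 11, concerning abnormalities in vital signs, serum creatinine". Section 7.8, on starting a new cycle, also cites only Table 11.

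Inclusion criterion 7e (synopsis and Section 5.2) reads "Serum creatinine ≤ 2.0 mL/dL and creatinine clearance ≥ 40 mL/min", where the creatinine unit is evidently a misprint for mg/dL. Table 13, footnote g, requires Run-in and Cycle 1 Day 1 chemistry to stay within the entry limits before treatment starts, and requires creatinine to be evaluated before each SL-401 dose.

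**The concern.** One pre-dose test should lead to one decision. Here a value above 1.8 and up to 2.0 mg/dL means hold under one list and no hold under the other two, and the site is not told which to follow.

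Both possible intentions cause trouble:

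- **If 1.8 is the intended limit**, a site working from Table 11 or the synopsis doses above it. The kidney is a known target organ. Section 3.4.2 reports renal tubular degeneration or necrosis in monkeys at 30 and 60 µg/kg/day, with one animal at 60 µg/kg/day euthanized because of it. Table 6 lists one attributed event of grade 3 or higher each for creatinine, renal failure and tubular necrosis among 92 patients.
- **If 2.0 is intended**, Section 7.7.2.3 withholds drug from patients whom the entry criteria admit. It makes re-dosing depend on the abnormality normalising, which a stable 1.9 may not do.

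In the Run-in Cycle this can reach the dose-escalation data, because Section 6.2.2 says that to be DLT-evaluable "a patient must receive all 5 doses within a 10 day time period". A persistent hold could leave a patient in a cohort of 3 to 6 non-evaluable. In either case, it is unclear which dosing decisions in the band are protocol deviations.

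**Working it through.** **1. The lists side by side.** The numeric limits shared by the synopsis, Table 11 and 7.7.2.3 are temperature, heart rate, systolic pressure, albumin below 3.0 g/dL, AST/ALT above 5 × ULN, weight gain and creatinine. All agree except creatinine. That pattern suggests a drafting error rather than two intended rules.

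**2. A patient at a stable 1.9 mg/dL, with clearance of at least 40 mL/min, through each rule.**

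| Rule | Limit (mg/dL) | Result on creatinine |
|---|---|---|
| Inclusion 7e | ≤ 2.0 | eligible |
| Table 13 footnote g, Run-in and Cycle 1 Day 1 | entry limit | may start |
| Synopsis hold list | > 2.0 | no hold |
| Table 11 | > 2.0 | no hold |
| Section 7.8, through Table 11 | > 2.0 | may start cycle |
| Section 7.7.2.3 | > 1.8 | withhold |

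If the value never moves, creatinine stops 0 of 5 infusions in a cycle under Table 11 and 5 of 5 under 7.7.2.3. This is a limiting case, not a forecast.

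**3. Can a patient enter in the band?** Criterion 7e also requires clearance of at least 40 mL/min. Solving the Cockcroft-Gault formula in Section 15.7 for the minimum weight W:

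W = 40 × 72 × Scr / (140 − age), divided by 0.85 for women.

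At Scr 1.9 the numerator is 40 × 72 × 1.9 = 5,472. The ages are assumptions; 66 is the median in Study 50047, which enrolled other diseases.

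| Age | Men | Women |
|---|---|---|
| 55 | 5,472 / 85 = 64.4 kg | 75.7 kg |
| 66 | 5,472 / 74 = 73.9 kg | 87.0 kg |
| 75 | 5,472 / 65 = 84.2 kg | 99.0 kg |

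Across the band at age 66, the minimum runs from 70.4 kg (men) and 82.9 kg (women) at 1.81 mg/dL to 77.8 kg and 91.6 kg at 2.0 mg/dL. Entry in the band is possible but limited. Others could qualify by 24-hour urine collection or rise into the band on treatment.

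**4. How often the rule is read.** A patient completing Cycle 6 has 5 × (1 + 6) = 35 scheduled pre-dose checks in phase 1, and 5 × 6 = 30 in phase 2, where there is no Run-in Cycle. There are more if infusions are postponed or treatment continues. These are occasions on which the rule is applied, not occasions in the band.

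**5. Reach into the DLT assessment.** Only the Run-in Cycle requires all 5 doses within 10 days. Section 6.2.2 asks for at least 3 SL-401 infusions in Cycle 1, and Section 11.2.1 defines evaluability more loosely (any study drug and follow-up through 2 cycles, or a DLT).

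**The case against.** The strongest reply is that the lists can be obeyed together. Each says when to hold, and none orders dosing below its limit. Sections 7.7 and 7.7.2.2 cite them jointly, so on a plain reading every listed hold applies and 1.8 governs as the stricter value. That reading is available, so divergence between sites is possible rather than certain. But the protocol nowhere states it, and it would leave the 2.0 limit in Table 11 with no effect, since any value above 2.0 is already above 1.8. A reader who follows the synopsis or Section 7.8 never meets the 1.8 limit. The stricter reading also clashes with the entry limit and the Day 1 check.

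Other points reduce the consequence without removing the conflict:

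- Section 11.2.1 replaces patients who are not evaluable for DLT, so the likely cost of a persistent Run-in hold is an extra patient or a delay, not a wrong escalation decision.
- The safety review committee looks at laboratory abnormalities on an ongoing basis, and Section 7.8 requires SL-401-related non-hematologic toxicity to return to grade 1 or baseline before a new cycle. Neither settles which limit applies to an infusion within a cycle.
- The number affected is unknown, and the weight thresholds rest on assumed ages.
- Sections 13.5 and 13.6 require ethics approval for changes affecting patient safety, so even a one-line correction carries amendment formalities.

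**Conclusion.** The inconsistency is real and should be fixed. Creatinine above 1.8 and up to 2.0 mg/dL calls for a hold under Section 7.7.2.3 and not under the synopsis or Table 11, and no rule of precedence resolves it. The conflict follows from the text alone and rests on no assumption. Its practical size cannot be estimated from the protocol: the band is 0.2 mg/dL wide, entry within it is restricted by the clearance criterion, and no endpoint or escalation rule uses the creatinine value. It matters because the rule is a safety stop read before every infusion of a drug with documented renal toxicity, and because a persistent Run-in hold could cost an evaluable patient. The protocol does not show which value was intended; 2.0 agrees with two of the three statements and with eligibility.

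**What to change.** State one hold limit in the synopsis, Table 11 and Section 7.7.2.3.

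- **Preferred:** change 7.7.2.3 to above 2.0 mg/dL. This is one line and agrees with inclusion 7e, the Day 1 check, Table 11 and Section 7.8.
- **If 1.8 mg/dL is the intended safety limit:** lower the synopsis hold list, Table 11 and inclusion 7e in both the synopsis and Section 5.2, four places in all. This also narrows eligibility, so it is a design change that the sponsor should decide on clinical grounds.

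Either route needs an amendment under Sections 13.5 and 13.6 and a short note telling sites which value applies. No new data or visits are required. In the same edit, as a separate clerical correction, change the creatinine unit in 7e from mL/dL to mg/dL.
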